Inclusion Criteria:	 Diagnosis of IPF, not established >5 years from the enrollment date, that fulfills ATS/ERS Consensus Criteria (1). Ability and willingness to give informed consent. Age 50-85 years old. Ambulatory. Presence of autoantibodies against HEp-2 cells at plasma titrations of ≥1:20, the assay for the primary endpoint. 				
Major Exclusion Criteria:	 Diagnosis of current infection, proven or suspected by participating physicians based upon their clinical assessments. Presence of active hepatitis B or C, or HIV infection. History of conventional autoimmune syndromes (e.g., systemic lupus erythematosus, scleroderma, rheumatoid arthritis, myositis, Sjogren's syndrome, anti-neutrophil cytoplasmic autoantibody vasculitis, Goodpasture's syndrome) by clinical evaluation or positive conventional autoimmune serologic tests (i.e., ANA, RF, Anti-Ro, ANCA, Anti-LA, Anti-RNP, Anti-Jo-1). History of reaction to murine-derived products or any of the trial medications, or prior exposures to human-murine chimeric antibodies. 				

- 5) Malignancy, excluding basal or squamous cell skin cancer or low-risk prostate cancer. The latter is defined as stage T1 or T2a with PSA less than 10 ng/dl. Rituximab is not known to promote cancer progression, and these criteria are within current guidelines.
- 6) Unwillingness to complete post-treatment surveillance for 9 months.
- Diagnosis of major morbidities (aside from IPF) expected to interfere with subjects' study participation for 9 months.
- 8) Treatment for >5 days within the preceding month with >10 mg. prednisone (or equivalent corticosteroid) or any treatment during the preceding month with a potent cellular immunosuppressant (e.g., cyclophosphamide, methotrexate, mycophenolate, azathioprine, calcineurin inhibitors, etc.).
- 9) Uncontrolled diabetes or hypertension that precludes safe treatment with methylprednisolone.
- 10) Concurrent participation in other experimental trials.
- 11) Pregnancy or unwillingness to use contraception during the duration of the study among female participants with child-bearing potential. The safety of rituximab during pregnancy has not been established.
- 12) Ratio of forced expiratory volume in 1 second to forced vital capacity (FEV₁/FVC) <70% of predicted values.

Study Endpoints:

· Primary endpoints:

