The primary endpoint is reduction of autoantibody titers to HEp-2 epithelial cells, comparing baseline measures of each individual to results of their interval measures during the next 9 months.

Secondary endpoints:

Secondary endpoints are: 1.) treatment-related effects on anti-HSP70 autoantibody concentrations, 2.) forced vital capacities, 3.) incidences of acute IPF exacerbations, 4.) survival durations; 5.) hospitalization rates; and 6.) adverse event-rates

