1. OBJECTIVE, SPECIFIC AIMS, BACKGROUND, AND SIGNIFICANCE

1.1 OBJECTIVE

The primary goal of this randomized, multi-center, double-blind Phase II clinical trial is to determine the effects of rituximab treatment in terms of autoantibody reductions (magnitude and duration) in IPF patients. We anticipate the findings here will lead to larger incremental trial(s) to determine actual clinical efficacy of this treatment.

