1.2 SPECIFIC AIMS

Hypothesis: Our central hypothesis is that antibody-mediated autoimmunity plays an important role in IPF progression. A corollary of this hypothesis is that treatments that reduce autoantibodies in these patients will have a favorable effect on the natural history of this disease. The studies proposed here are primarily designed to determine the magnitude and duration of autoantibody reductions affected by rituximab, as a prelude to design of a definitive Phase III efficacy study. Nonetheless, we hope that experimental treatments may result in clinically-relevant beneficial effects as determined by secondary endpoints: preservation of forced vital capacities or reductions of acute exacerbation incidences.

Specific Aims:

1. To conduct a proof-of-concept, mechanistically-driven trial to reduce autoantibodies against epithelial HEp-2 cells among IPF patients.

We hypothesize the experimental treatment with rituximab will more effectively reduce anti-HEp-2 autoantibodies, the primary endpoint of this clinical trial, compared to placebo treatment.

To determine the effects of the experimental rituximab treatment on secondary endpoints of anti-HSP70 autoantibodies, preservation of forced vital capacities, survival, need for hospitalizations, incidences of acute IPF exacerbations, and adverse event-rates.

We hypothesize the experimental treatment will also have a demonstrable effect on these secondary endpoints, in comparison to placebo therapy, and will have acceptable adverse event profile.

Findings of this study will also further develop the potential of focused immunologic assays as prognostic and disease phenotyping tools of individual IPF patients. We anticipate this proposal will establish the feasibility of autoantibody-targeted interventions, and results here will be a nidus for subsequent incremental clinical trials in this population.

The preliminary data that support our central hypothesis are novel findings from a series of innovative investigations.

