2.8 STUDY ENDPOINTS

2.8.1. The Primary End-Point

The primary end-point is reduction of autoantibody titers to HEp-2 cells, using indirect immunofluorescence (IFA), from baseline to the nine-month assessment point.

HEp-2 Autoantibody Titers: IFA methods to detect and quantify autoantibodies have been detailed by us previously (10,14). In brief, commercially available HEp-2 slide wells are incubated with titered dilutions of subject plasma (i.e., at 1:20, 1:40, 1:80, etc). After washing, the bound autoantibodies are detected with the secondary mAb (FITC-conjugated anti-human IgG). IPF specimens will be scored as positive if fluorescence intensity at titers ≥1:20 is greater than that of concurrent normal plasma specimens (determined by imaging in a fluorescent microscope) (14).

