2.9 DATA AND POWER ANALYSES

2.9.1 Power Analyses:

Given the initial nature of this trial, definitive power calculations are speculative. Nonetheless, even moderate efficacy of the experimental treatment (as we anticipate) will produce evidence of same. Assuming a type 1 error rate of 0.05, a two-sided alternative hypothesis, n = 29/arm, and very conservative event rates (i.e., reduction of autoantibody titers in 33% of the experimental arm subjects, and 3% reduction in placebo controls) there is 80% power to detect a statistically significant effect.

The sample size of 58 for this clinical trial is based on exposing a minimum number of patients to potential risks of the experimental treatment, while still obtaining useful information. Analyses will follow intention to treat principles. Missing data techniques (e.g., multiple imputation) will be employed for subjects lost to follow-up, had transplants, or those who died. A sensitivity analysis will also be conducted in which transplantations and deaths will be considered failures.

2.9.2 Data Analyses:

Data analyses begin by describing baseline demographic and medical characteristics of the cohorts. Descriptive statistics, including measures of central tendency and dispersion, will be computed for continuous data (e.g., age). Frequency distributions will be estimated for categorical data (e.g., gender). To ensure balanced random assignments, treatments are examined in relationship to demographic and medical characteristics using the appropriate parametric (e.g., t-test) or nonparametric test (e.g., chi-square, Wilcoxon tests). Reduction of autoantibody titers from baseline to the nine-month follow-up visit will be calculated as a binary indicator (yes/no). A Fisher's Exact test will be used to compare rates of autoantibody titer reductions between the two groups. To control for the stratification variables, an exact logistic regression model will be used, including main effect for treatment and the stratification variables. Unbalanced baseline characteristics will also be included in the regression model.

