2.10 ANTICIPATED RESULTS AND PITFALLS

2.10.1. Primary Endpoint:

By analogy to other rituximab-treated disease populations (29-39) we hypothesize the experimental treatment will result in reductions of autoantibodies. We are less certain of the time-to onset, magnitude, and duration of these effects in IPF patients, which is a primary goal of this trial.

We do not expect technical pitfalls, being very proficient with the anti-HEp-2 assays. To clarify, however, we are using these assays to detect nonspecific patterns that are not diagnostic for SLE, scleroderma, etc. (see Fig. 4 and citation 14). IPF patients with classic ANA tests diagnostic for SLE or other known autoimmune disorders will not be eligible for enrollment.

Findings herein of early autoantibody reappearances (e.g., within <6 months) would indicate that sequential, repeated rituximab dosing might be necessary in later definitive trials to test for clinical efficacy in IPF patients, or perhaps even warrant considerations for addition of a second agent (e.g., belimumab).

2.10.2. Secondary Endpoints:

We are proficient with ELISA and do not anticipate technical problems with the anti-HSP70 assays. We are able to reproducibly measure anti-HSP70 in all IPF plasma specimens, even when concentrations are <<mean normal values, and anticipate having serial, quantitative assay measures in all subjects. We expect rituximab will result in anti-HSP70 reductions, compared to controls, but pharmacodynamics of the effects remain to be determined.

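### The plan makes the size and duration of the HEp-2 titre fall a primary goal, but the only committed HEp-2 analysis is a month-9 yes/no that shows neither its size nor its course

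*Combined protocol and SAP*

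**What the plan says.** **Goal.** Section 1.1 sets out to "determine the effects of rituximab treatment in terms of autoantibody reductions (magnitude and duration) in IPF patients". Section 1.2 calls the studies "primarily designed to determine the magnitude and duration of autoantibody reductions affected by rituximab". Section 2.10.1 says the investigators are less certain of the "time-to onset, magnitude, and duration of these effects in IPF patients, which is a primary goal of this trial", and it treats reappearance of autoantibodies before six months as informative for later trials. Section 1.4 calls these data essential for Phase III design.

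**Endpoint.** The synopsis (Study Endpoints) defines the primary endpoint by "comparing baseline measures of each individual to results of their interval measures during the next 9 months". Section 2.8.1 defines it as the reduction in titre "using indirect immunofluorescence (IFA), from baseline to the nine-month assessment point". Titres are read from "titered dilutions of subject plasma (i.e., at 1:20, 1:40, 1:80, etc"), and the synopsis requires for entry "Presence of autoantibodies against HEp-2 cells at plasma titrations of ≥1:20, the assay for the primary endpoint".

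**Analysis.** Section 2.9.2: "Reduction of autoantibody titers from baseline to the nine-month follow-up visit will be calculated as a binary indicator (yes/no"). Rates are compared by Fisher's exact test, with exact logistic regression to adjust for the stratification variables. Linear regression is committed for continuous secondary endpoints. Mixed-effects models appear only among exploratory analyses that *may* be used.

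**Power.** Section 2.9.1 assumes 29 per arm, two-sided 0.05, and reduction in 33% of rituximab and 3% of placebo patients. It calls these rates very conservative and states 80% power.

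**The concern.** A yes/no at one visit answers a narrower question than the one the trial sets itself. It gives two responder rates and an odds ratio at month 9. It does not say whether titres fell by one dilution or four, or when they fell and returned. HEp-2 is the primary marker, and its month 1, 3 and 6 titres hold most of the information on onset and duration, yet no method is fixed for them.

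Two further gaps sit beside this. The synopsis and Section 2.8.1 describe different endpoints, and no section says how large a fall counts as a reduction. The assumed placebo rate of 3% therefore has no responder definition behind it. At stake is whether the trial delivers the magnitude and duration estimates that it says Phase III needs, and how far its stated power can be relied on.

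**Working it through.** **1. Is any analysis of the serial HEp-2 titres committed?**

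| Place | What it offers | Covers HEp-2 size or course? |
|---|---|---|
| 2.6.2 Table 2; 2.7.1 | HEp-2 sampled before treatment and at months 1, 3, 6, 9 | Data collected |
| 2.8.1; 2.9.2 | Yes/no, baseline to month 9 | Presence at month 9 only |
| 2.8.2(a) | Says effects on the primary endpoint and on anti-HSP70 can be tested, and lists the serial visits | Intention, no method |
| 2.9.2, linear regression | Continuous secondary endpoints | No; this reaches anti-HSP70 |
| 2.9.2, exploratory | Mixed models *may* be used for the outcomes | Optional; HEp-2 not named |

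**2. Are the two endpoint wordings the same?** No. One possible reading of the synopsis is a fall at any visit. With a 3% chance of a placebo fall at each of four visits, assumed independent, the rate would be 1 − 0.97⁴ = 11.5%, not 3%.

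**3. Reproducing the stated power.** Inputs from 2.9.1: n = 29 per arm, two-sided α = 0.05, rates 0.33 and 0.03. Exact Fisher power is

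Σₓ Σᵧ Bin(x; 29, p_T) · Bin(y; 29, p_C) · 1{Fisher p ≤ 0.05} = **81.0%**

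(79.6% for 1/3 against 1/29). The stated 80% is sound.

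**4. Dependence on the placebo rate.** Let r be the true response among patients who would not have scored yes anyway: 0.33 = 0.03 + 0.97r, so r = 0.30/0.97 = 0.309. For another placebo rate p₀ the treated rate is p₀ + (1 − p₀)r. Rates other than 3% are assumptions.

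| Placebo rate | Treated rate, same r | Power, same r | Power, treated fixed at 33% | Power, 30-point difference kept |
|---|---|---|---|---|
| 3% | 33.0% | 81.0% | 81.0% | 81.0% |
| 5% | 34.4% | 74.8% | 70.7% | 76.6% |
| 10% | 37.8% | 61.5% | 45.3% | 68.1% |
| 15% | 41.3% | 50.8% | 25.5% | 62.2% |
| 20% | 44.7% | 41.5% | 12.9% | 57.2% |

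On all three conventions power falls as the placebo rate rises, so 3% is on the favourable side.

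**5. What would 3% require?** The documents give no assay repeatability or titre distribution, so this is illustration. Assume true log2 titre is normal (mean 1.5 and SD 1.5 in steps above 1:20), patients are selected for a reading of at least 1:20 (about 25% then enter at 1:20), readings are floored to doubling steps, and reading error is independent. With reading SD 0.05, 0.25, 0.35 and 0.50 log2 and no true change, 3%, 15%, 21% and 28% of placebo patients read at least one step lower. If any lower titre counts, 3% needs almost no reading variation.

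**6. Should a log2 analysis replace the Fisher test?** Same model, with a month-9 baseline-adjusted comparison (ANCOVA) standing in for the month-9 contrast of a repeated-measures model. Power at reading SD 0.05/0.25/0.35/0.50:

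| Scenario | One-step Fisher | Two-step Fisher | ANCOVA on log2 titre |
|---|---|---|---|
| One third fall one step | 84/43/30/18% | – | 88/49/41/30% |
| One third fall two steps | 86/57/45/33% | 74/65/57/42% | 95/79/71/59% |
| One third fall two steps, about 7% enter at 1:20 (SD 0.25/0.35 only) | – | 84/77% | 83/76% |

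With 10% or 20% random losses (SD 0.35, one third falling two steps), and losses counted as failures, Fisher has 38% or 33% (one-step) and 46% or 36% (two-step). A rank analysis placing losses worst has 36% or 21%.

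The gain is therefore 4 to 12 points in the first row, larger in the second, nil in the third, and gone when losses are ranked worst. As a description the log2 analysis is still useful: in the second scenario it estimates a month-9 difference of about 0.6 log2 to within ±0.34 to ±0.50 log2.

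**The case against.** **Reduction has a plain meaning.** On a doubling-dilution scale, any lower titre is one step down, and a patient entering at 1:20 can meet that by turning negative. This stands. A reader might infer that two analysts, one using a one-step and one a two-step rule, would reach different primary results. No section contains a two-step rule, so how often the two would disagree says nothing about this plan. What remains is that the rule should be written down.

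**The serial titres are not ignored.** Section 2.8.2(a) ties the primary endpoint to serial testing, and 2.9.2 says exploratory analyses will be done. This stands in part. It would be wrong to say that no analysis is mentioned, but no method or contrast is fixed.

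**Month 9 does inform duration.** It shows whether a reduction persists at nine months, which is a legitimate primary question, and exploratory description suits an early-phase trial. That supports keeping month 9 primary. It does not supply size, onset or time of return, which 2.10.1 names as a primary goal.

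**Power is called speculative, and batching may limit noise.** Section 2.9.1 does hedge, and its very conservative label covers the pair of rates. Batched assays (2.7.1) and concurrent normal plasma (2.8.1) may reduce reading variation. Both are fair. Neither makes a 3% placebo rate conservative.

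**Conclusion.** The point holds as a mismatch between the primary goal and the committed analysis. It rests on the text alone: the HEp-2 analysis is a month-9 yes/no, the other visits have no committed method, the synopsis wording differs, and no size of fall is stated. It should be fixed, and it does not invalidate the design.

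The power figures are conditional. The 81.0% is exact for the plan's own rates. The fall to between 74.8% and 41.5% assumes placebo rates of 5% to 20% and an unchanged true response.

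Three stronger conclusions might be inferred and are not supported:

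- *The stated power is wrong.* It reproduces. Only its label and its single scenario are at fault.
- *The Fisher test must give way to a log2 analysis.* The gain depends on assumed noise, titre distribution and effect size. It is small if one third fall one step, absent against a two-step rule at SD 0.25 and 0.35 when few enter at 1:20, and disappears when losses are ranked worst.
- *The open cut-off inflates type I error.* In simulation with no effect, choosing the better of a one-step and a two-step cut-off afterwards kept rejection at or below 3%.

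**What to change.** 1. Use one primary endpoint definition, baseline to month 9, in the synopsis, 2.8.1 and 2.9.2. State that a reduction means at least one doubling-dilution step lower, with 1:20 to negative counted as one step, or state another rule.
2. Keep the month-9 Fisher test and exact logistic regression as primary. Commit to a supporting baseline-adjusted repeated-measures model of log2 HEp-2 titre (negative at 1:20 coded one step below) with the stratification factors. Report the treatment difference and confidence interval at months 1, 3, 6 and 9.
3. Add a rank or ordinal sensitivity analysis, because titres are stepped and floored. Say how the death and transplant rules in 2.9.1 apply to titres.
4. Drop the very conservative label for the 3% placebo rate and show power over a range of placebo rates, as in the table above.

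Cost: wording and a little more analysis. All titres are already scheduled, so no visit or blood draw is added. A ratio of geometric means is harder to explain than a responder percentage, which is one reason to keep the responder comparison in front.

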2.4 RANDOMIZATION

Following a determination of eligibility, subjects will be randomly assigned to one of two treatment arms (1:1 ratio), after stratification on the basis of gender, disease severity (DLCO <35% of predicted values), and current use of either/both pirfenidone and/or nintedanib. These stratifications will ensure ~equal proportions of severely ill patients, and ~equal proportions of males, in each arm. Male IPF patients have worse prognoses than females (1-4). Randomization assignments will be made in random block sizes of 2 and 4.

Randomizations will occur on the day of initial treatment, to reduce the possibility of "wasting" a randomization on a patient who fails to return for treatment.

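### The binary primary endpoint has two tests and no rule for which decides; Boschloo's exact test would hold size at 0.05 and give about 0 to 8 points more power than Fisher's.

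*Combined protocol and SAP*

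**What the plan says.** Section 2.9.2 reduces the primary endpoint to a binary indicator of titer reduction from baseline to nine months. It then says "A Fisher's Exact test will be used to compare rates of autoantibody titer reductions between the two groups", and in the next sentence "To control for the stratification variables, an exact logistic regression model will be used, including main effect for treatment and the stratification variables". A further sentence adds to that model any baseline characteristics found to be unbalanced, with no list and no threshold. Neither analysis is called primary, supportive or sensitivity. The only analysis labelled as sensitivity, in section 2.9.1, counts transplantations and deaths as failures.

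The power statement in section 2.9.1 names no test. Its inputs are "Assuming a type 1 error rate of 0.05, a two-sided alternative hypothesis, n = 29/arm", with "reduction of autoantibody titers in 33% of the experimental arm subjects" and "3% reduction in placebo controls", from which it concludes that "there is 80% power to detect a statistically significant effect". Section 2.4 randomizes "after stratification on the basis of gender, disease severity (DLCO <35% of predicted values), and current use of either/both pirfenidone and/or nintedanib", in random blocks of 2 and 4.

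**The concern.** Two analyses of one endpoint with no stated precedence leave the primary conclusion open if they fall on opposite sides of 0.05. One of them is also not fully specified in advance, because its covariates depend on which imbalances are seen.

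The choice of Fisher's test raises a separate issue of efficiency. Section 2.9.1 justifies 58 subjects as the fewest that can be exposed to risk while still yielding useful information. A test that uses only about half of its permitted type I error fits poorly with that aim when another exact test, on the same data, uses nearly all of it.

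**Working it through.** **Inputs.** From section 2.9.1: two-sided alpha 0.05, 29 per arm, response rates 0.33 (rituximab) and 0.03 (placebo), stated power 80%. From section 2.4: 1:1 allocation, three stratification factors (8 strata), blocks of 2 and 4.

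**Step 1. Reproduce the stated power.** Let *a* and *b* be the responders on rituximab and placebo. Power is the sum over all (*a*, *b*) with Fisher p ≤ 0.05 of Bin(*a*; 29, 0.33) × Bin(*b*; 29, 0.03). Fisher's two-sided p sums the hypergeometric probabilities no larger than that of the observed table. Result: **0.810**, so the stated 80% is reproduced. The uncorrected normal approximation (pooled variance) gives 0.865 and does not match.

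**Step 2. Fisher's true size.** Size is the maximum over a common rate π of the sum over the same region of Bin(*a*; 29, π) × Bin(*b*; 29, π). Result: **0.025**. With equal arms the two-sided Fisher p is twice the one-sided p, so each conditional tail is capped at 0.025, and discreteness lowers it further.

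**Step 3. Boschloo's test.** Use Fisher's p as the ordering statistic and reject when p ≤ *c*, where *c* is the largest value that keeps the maximum size over π at or below 0.05. At 29/29, *c* = 0.082, the maximum size is **0.048** and the power is **0.889**. The gain is 0.889 − 0.810 = 0.079.

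The gain comes from tables that Boschloo rejects and Fisher does not:

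| Responders, rituximab v placebo | Fisher p | Probability at 33% v 3% |
|---|---|---|
| 5 v 0 | 0.0518 | 0.0129 |
| 7 v 1 | 0.0517 | 0.0368 |
| 8 v 2 | 0.0787 | 0.0216 |
| 10 v 3 | 0.0563 | 0.0068 |
| 11 v 4 | 0.0700 | 0.0012 |
| 12 v 5 | 0.0819 | 0.0001 |

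These sum to 0.0794, which agrees with 0.079 within rounding.

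**Step 4. Other splits of 58.** Blocks within 8 strata do not guarantee 29/29, so the calculation was repeated:

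| Rituximab/placebo | Fisher | Boschloo | Gain | Fisher maximum size |
|---|---|---|---|---|
| 29/29 | 0.810 | 0.889 | 0.079 | 0.025 |
| 30/28 | 0.841 | 0.890 | 0.049 | 0.037 |
| 31/27 | 0.867 | 0.903 | 0.036 | 0.037 |
| 28/30 | 0.898 | 0.906 | 0.008 | 0.037 |
| 27/31 | 0.885 | 0.885 | 0.000 | 0.037 |

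The gain cannot be negative. Fisher's size never exceeds 0.05, so *c* is at least as large as Fisher's own cut-off and Boschloo's rejection region contains Fisher's.

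**Step 5. Does stratification explain the loss?** Boschloo's test also ignores the strata, so the gain in step 3 cannot come from using them. The documents give no stratum prevalences beyond an expectation of about 40% women (section 3.1), and no prognostic effects, so these had to be assumed. A simulation of 6,000 trials with stratified blocks assumed prevalences of 60%, 35% and 50% for the three factors. It compared Fisher with an exact test stratified on all 8 strata, as a stand-in for exact logistic regression:

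- strata not prognostic: 85.2% stratified, 84.9% Fisher (+0.3 points)
- log-odds of 1 per factor: 88.3% stratified, 86.0% Fisher (+2.3 points)

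The Monte Carlo standard error is √(0.85 × 0.15 / 6,000) ≈ 0.5 point. A smaller simulation of 400 to 600 trials, using the exact logistic model itself under assumed strata, gave 0.84 to 0.87 against 0.84 for Fisher. Its standard error is about 1.5 to 1.8 points. Adjustment therefore recovers about 0 to 3 points.

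**Step 6. How often would the two planned tests disagree?** In the smaller simulation they disagreed in 3% to 4% of trials at 33% v 3%. Under equal rates of 15%, at least one of the two rejected in 0.043 of trials.

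**The case against.** The plan can be read as settling the matter already: Fisher comes first, the stated power matches it, and the regression follows as an adjusted analysis. That reading is natural, but the text does not state it. Because randomization is stratified, a reader could equally take the adjusted model as decisive.

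Fisher is a standard choice, this is a proof-of-concept biomarker trial whose power is described as speculative, and the planned power is met. All of that stands. It limits the point to efficiency and clarity and does not remove it.

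Four stronger readings are tempting, and the evidence does not support them:

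- *The trial falls short of its stated power.* It does not: Fisher gives 0.810. The difference from Boschloo is power forgone.
- *Fisher loses power because it ignores the strata.* Step 5 shows that the loss comes from conditioning and discreteness.
- *Making the exact logistic model decisive would recover the 8 points.* It recovers about 0 to 3, under assumed strata.
- *Choosing between the tests inflates the false-positive rate.* This is not shown. In the one null case examined, taking either test rejected in 0.043, below 0.05. That run used the stratification variables and says nothing about adding covariates after imbalance is seen.

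**Conclusion.** The point holds as a worthwhile improvement, not as an error in the planned power. The missing precedence rule is mainly a labelling gap, since the two tests would disagree in roughly 1 trial in 30. It is made worse by a model whose covariates are left open.

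The more substantial part is the choice of exact test. At the protocol's own inputs, Boschloo's test holds size at or below 0.05 and adds about 0 to 8 points of power over Fisher, depending on the realized split of 58.

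The power figures rest on response rates of 33% and 3%, an observed or imputed outcome for every subject, and the usual two-sided Fisher p-value. The disagreement rate and the 0 to 3 points for the logistic model rest on assumed stratum prevalences and effects that the documents do not give.

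**What to change.** Before unblinding, amend section 2.9.2 to:

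1. Name Boschloo's exact unconditional test, two-sided at 0.05, as the single decisive test of the primary endpoint, in place of Fisher's.
2. Label the exact logistic model as supportive, with treatment and the three randomization factors (gender, DLCO below 35% predicted, antifibrotic use) as its only covariates, and drop the open-ended addition of unbalanced characteristics.

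If the sponsor prefers the exact logistic model as decisive, the same three covariates should be fixed in advance, and only about 0 to 3 points over Fisher should be expected.

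Neither option needs extra subjects or data. The power sentence in section 2.9.1 must name the chosen test and be re-based on it. The plan must also say how that test's p-value is obtained across multiply imputed data sets. The present plan leaves this unstated for Fisher and exact logistic regression too, so the second task is not created by the change.
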